Resident outcomes include key factors that contribute to aging in place, including a primary outcome of functional status and secondary outcomes of quality of life, depression, and health care utilization. We will measure function using 2 measures. The Short Physical Performance Battery (SPPB) is an objective measure of lower extremity functioning in older adults which has excellent reliability, validity, and responsiveness (range, 0-12 points).^{80,92} We will also measure self-reported ability to perform 8 ADLs using the Yale ADL scale (range, 0-16).⁶⁸⁻⁷¹ We will assess quality of life using the Quality of Life in Alzheimer's Disease (QOL-AD) scale⁸¹ and depression using the Patient Health Questionnaire (PHQ-9).⁸² Health care utilization will be assessed by self-report. Other outcomes will include adverse events and attitudes about function and physical activity (see Table 3).⁸³⁻⁸⁷ Home care

worker outcomes will include knowledge⁸⁸ and attitudes about Function-Focused Care⁸⁷ and job satisfaction.⁸⁹ For family caregivers, outcomes will include quality of life,⁹⁰ depression,⁸² and caregiver burden.⁹¹

Analysis plan and power calculation: We will analyze measures of feasibility using similar methods to Aim 2. We will define the intervention as feasible if residents complete $\geq 75\%$ of checklist items. For other outcomes, we will assess change from baseline to 2 months and compare the changes between intervention and waitlist groups. For continuous outcomes, the change will also be continuous; for dichotomous outcomes, the change can be defined as a four-category variable (0-0, 0-1, 1-0, and 1-1 for pre and post outcomes). We will then compare the change between intervention and waitlist groups using the t-test or Wilcoxon signed rank sum test for continuous variables and Chi-square or Fischer's exact test for dichotomous variables.

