Because this is a pilot feasibility study, the sample size need only be large enough to determine key parameters such as recruitment, retention, and refusal rates. Given the pool of potential participants, we are confident that we can recruit enough participants to not only determine feasibility but also determine point estimates and standard deviations for projected sample size for a follow-up randomized controlled trial. We plan to recruit a total of 70 participants in the overall study. To estimate preliminary effect sizes, the mean scores for continuous outcomes or proportions for dichotomous outcomes will be compared among participants in the intervention vs. waitlist control conditions. If we assume that the correlation between pre and post continuous measures from baseline to 6 months is 0.8, then the SD for the change is 0.6 SD for the continuous measures. With 70 residents, we will have 80% power (2-sided alpha of 0.05) to detect a 0.66 SD change in the mean of continuous measures from baseline to 2 months, assuming a 20% dropout. Thus, for our primary outcomes, we should have sufficient power to detect a mean 1.78-point increase in SPPB score (SD~2.7)⁹¹ and a mean 1.45-point increase in ADL/IADL score (SD~2.2).⁷⁶

Potential problems and alternative approaches: Potential problems include staff turnover, resident loss to follow-up, and a relatively limited sample size and follow-up period. We will train new staff and champions and use best practices to minimize loss to follow-up, including obtaining multiple types of contact information at baseline and providing sequential incentives for participation. Also, our implementation protocol will incorporate stakeholder input on barriers and facilitators to implementation identified in Aim 1. Although this pilot study has a limited sample size, it will provide preliminary data to support a definitive R01-level study.

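### The effect-size sentence compares mean scores or proportions between arms, while the analysis plan and power inputs use change from baseline; one quantity should be stated for both

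*Combined protocol and SAP*

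**What the plan says.** All the relevant text is in the combined protocol and SAP, Aim 3, under *Analysis plan and power calculation*.

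- **Analysis paragraph.** For outcomes other than feasibility, "we will assess change from baseline to 2 months and compare the changes between intervention and waitlist groups". For dichotomous outcomes, "the change can be defined as a four-category variable (0-0, 0-1, 1-0, and 1-1 for pre and post outcomes"), tested by chi-square or an exact test.
- **Sample-size paragraph, effect sizes.** The preliminary estimates are described thus: "the mean scores for continuous outcomes or proportions for dichotomous outcomes will be compared among participants in the intervention vs. waitlist control conditions".
- **Sample-size paragraph, power.** The next sentence assumes that "the correlation between pre and post continuous measures from baseline to 6 months is 0.8", and concludes "then the SD for the change is 0.6 SD for the continuous measures". The detectable effect is again put in terms of change: the study is powered "to detect a 0.66 SD change in the mean of continuous measures from baseline to 2 months".

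The *Outcome measures* paragraph has both arms measured at baseline and 2 months, and the waitlist arm again at 4 months. No passage specifies adjustment for the baseline value.

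**The concern.** The test and the power inputs rest on change. The one sentence about estimating effect sizes names a different quantity: scores or proportions by condition. It does not say which of the planned measurement times is meant or whether baseline enters.

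Two analysts could follow this plan and report different effect sizes. One would report a difference in 2-month means, the other a difference in mean change. The two can differ in size, and in a small study in sign, so the reported effect size could fail to match the reported test. For dichotomous outcomes the mismatch is sharper, because a four-category change variable has no single proportion to compare.

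The plan says the pilot will supply point estimates and SDs for sizing a later randomised trial. The SD of a score and the SD of a change are different inputs to that calculation, and the plan does not say which goes with the effect size.

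**Working it through.** **Inputs from the sample-size paragraph.** Total 70; dropout 20%; correlation ρ = 0.8 (stated for baseline to 6 months); SD of change 0.6 SD; two-sided alpha 0.05; power 80%; detectable change 0.66 SD; SDs of 2.7 (SPPB) and 2.2 (ADL). Completers: 70 × 0.8 = 56, or 28 per arm at 1:1. The 15 buildings cannot split exactly in half; a 7:8 split hardly alters the results.

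**The plan's own figures.**
- The point conversions reproduce: 0.66 × 2.7 = 1.78 and 0.66 × 2.2 = 1.45. So 0.66 is in units of the score SD.
- The SD of change is √(2(1 − 0.8)) = 0.632 SD, against 0.6 stated. The value 0.6 equals √(1 − 0.8²), the SD after adjustment for baseline, although the text labels it the SD of the change.
- The 0.66 does not reproduce. With 28 per arm and SD 0.6, (1.960 + 0.842) × 0.6 × √(2/28) = 0.45 SD (0.46 by t-test). A t-test with 14 per arm and SD 0.6 gives 0.66. This is a separate matter, and nothing below depends on it.

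**Variance of each candidate estimate.** Take equal SDs at the two times, set to 1, and individual-level data. A 2-month score is ρ × baseline plus a residual with variance 1 − ρ². At ρ = 0.8:
- 2-month score: 0.64 (from baseline) + 0.36 (residual) = 1.00
- change: (0.8 − 1)² + 0.36 = 0.04 + 0.36 = 0.40
- 2-month score adjusted for baseline: 0.36

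The 0.64 is the chance baseline difference passing into the 2-month comparison. Imbalance and extra variance are therefore one thing.

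SE = √(variance × 2/28); half-width = 1.96 × SE; points = half-width × 2.7 or 2.2.

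| Estimate | Variance | SE (SD) | 95% half-width (SD) | SPPB points | ADL points |
|---|---|---|---|---|---|
| 2-month scores | 1.00 | 0.267 | 0.52 | 1.41 | 1.15 |
| Change, exact SD 0.632 | 0.40 | 0.169 | 0.33 | 0.89 | 0.73 |
| Change at the plan's 0.6, or baseline-adjusted | 0.36 | 0.160 | 0.31 | 0.85 | 0.69 |

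Variance ratio, scores to change: 1/0.40 = 2.5, or 1/0.36 = 2.8 with the plan's 0.6.

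**Dependence on the correlation.** Scores against change: 1/(2(1 − ρ)). Scores against the adjusted estimate: 1/(1 − ρ²).

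| ρ | Against change | Against adjusted |
|---|---|---|
| 0.5 | 1.0 | 1.33 |
| 0.7 | 1.67 | 1.96 |
| 0.8 | 2.5 | 2.78 |
| 0.9 | 5.0 | 5.26 |

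**Dependence on clustering.** With 56/15 = 3.73 completers per building (equal sizes assumed), the design effect is 1 + 2.73 × ICC. The documents give no ICC. Taking 0.01 to 0.3 as an assumed range, it runs from 1.03 to 1.82. If scores and change had the same ICC, the ratio would stay at 2.5. At opposite ends of the range it would lie between 2.5 × 1.03/1.82 = 1.4 and 2.5 × 1.82/1.03 = 4.4.

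**Which SD is carried forward.** The plan's 0.66 score SDs is 0.66/0.632 = 1.04, or 0.66/0.6 = 1.10, SDs of change. An effect size reported without its standardising SD cannot be used safely.

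**The case against.** The strongest reply is that the sentence is loose shorthand. The introduction to Aim 3 describes the design as examining change, the analysis paragraph specifies change, and the sentences straight after the quoted one give the SD of change and a detectable change. On that view mean scores are mean change scores, and proportions are those in the four change categories, which a chi-square test does compare. This stands in part: the text does not say that 2-month scores alone will be used or that baseline will be ignored. But the sentence is the only instruction on estimating effect sizes, its plain sense is outcome levels by arm, and nothing in the plan settles the matter.

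A reader might go further and infer that the reported effect size will carry baseline imbalance and also 2.5 to 2.8 times the variance. The documents do not support that. It turns one reading into fact and counts one thing twice: under randomisation a chance baseline gap is where the extra variance comes from, not a further bias.

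A reader might also take the effect size to be the pilot's chief product. The sample-size paragraph puts feasibility rates first and adds point estimates and SDs as a further aim.

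Two other objections stand. The 0.8 is stated for 6 months, while the comparison is at 2 months. And a raw change score is not free of baseline imbalance: at ρ = 0.8 a baseline gap enters with weight 0.8 − 1 = −0.2. That is why the fix puts baseline adjustment first.

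**Conclusion.** The inconsistency is real and should be corrected. It is a matter of wording with a conditional consequence, not an established defect in the estimate.

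If the sentence is followed literally with 2-month scores, the preliminary effect size has about 2.5 to 2.8 times the variance of a change-based one, and its 95% half-width for SPPB is 1.41 points in place of 0.85 to 0.89. This assumes a 2-month correlation of 0.8, equal SDs at the two times, 28 completers per arm and no allowance for clustering. At a correlation of 0.5 the penalty against change disappears; at 0.9 it is fivefold. Site-level correlations, which are not stated, could move it either way. If the sentence was meant as change, there is no loss of precision and only the wording needs repair.

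**What to change.** Replace the effect-size sentence with one along these lines:

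> *Preliminary effect sizes are the between-arm difference at 2 months adjusted for the baseline value, in points and divided by the pooled baseline SD, with 95% confidence intervals.*

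The between-arm difference in change from baseline to 2 months would serve the same purpose and stays closest to the analysis paragraph. At a correlation of 0.8 the two differ little (SD 0.6 against 0.632). The adjusted form is never less precise in the calculation above, setting aside the one degree of freedom spent on the baseline term, and it removes the residual −0.2 weight on the baseline gap. Whichever is chosen should also be the quantity tested in the analysis paragraph.

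Report the observed SD of change and the observed pre-post correlation at 2 months beside the effect size, so that the later trial can be sized on either basis.

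For dichotomous outcomes, name one comparison that uses baseline status, such as 2-month proportions by arm adjusted for or stratified by baseline status. Use it in both paragraphs, either replacing the four-category test or keeping the four categories as description only.

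The cost is wording. Baseline and 2-month measurements are already planned in both arms, and no visit, measure or participant is added.

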Improving Aging in Place for Older Adults Living in Subsidized Housing

NCT04212442

July 1, 2020

Aim 3: Determine the feasibility and preliminary effectiveness of the adapted Function-Focused Care intervention in subsidized housing residents at high risk for nursing home admission. We will conduct a 2-month pilot test of the adapted Function-Focused Care intervention in 15 subsidized apartment buildings for older adults. We will use a pre-to-post study design to examine the change in outcome measures from baseline to 2 months. Implementation outcomes will include feasibility and acceptability. Preliminary effectiveness outcomes will include resident function (primary outcome), with secondary outcomes of quality of life and health care utilization. Because function declines over time, our design will incorporate a waitlist control, in which half of the sites are cluster randomized to receive the intervention in months 0-2 while the other sites are randomized to receive usual care. The waitlist sites will then receive the intervention in months 2-4. The waitlist period will provide a baseline rate of functional decline that will serve as a comparison for functional outcomes (see Figure 3 for study flow).

Study setting and population: We will pilot the intervention in 15 subsidized apartment buildings for older adults.

Eligibility: Residents living at any of the sites will be invited to participate. If a resident wishes to participate but does not pass consent verification,⁶⁷ they will be asked to sign an assent to participate, and a proxy will be contacted to complete the consent process. Residents will receive sequential \$50 incentives for participation at baseline, 3, and 6 months (i.e., up to \$150 total).

[figure not shown]

Figure 3.

resident-family caregiver dyads, among residents who have such support.

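### The stated detectable effect of 0.66 SD does not follow from the plan's own inputs, which give 0.46 to 0.48 SD before clustering; clustering by building is left out

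*Combined protocol and SAP*

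**What the plan says.** All the inputs stand in the Analysis plan and power calculation section. It assumes that "the correlation between pre and post continuous measures from baseline to 6 months is 0.8, then the SD for the change is 0.6 SD", and it concludes: "With 70 residents, we will have 80% power (2-sided alpha of 0.05) to detect a 0.66 SD change in the mean of continuous measures", allowing for 20% dropout. It then converts the effect into points for the two co-primary measures: "we should have sufficient power to detect a mean 1.78-point increase in SPPB score (SD~2.7"), and 1.45 points on an ADL/IADL score with an SD of about 2.2.

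The same section names the comparison: "We will then compare the change between intervention and waitlist groups using the t-test or Wilcoxon signed rank sum test for continuous variables". The Aim 3 design paragraph sets the unit of allocation, stating that "half of the sites are cluster randomized to receive the intervention in months 0-2", with 15 buildings in all. No ICC, design effect or building-size assumption appears anywhere.

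The section also says that "the sample size need only be large enough to determine key parameters such as recruitment, retention, and refusal rates". The 70 residents are therefore justified by feasibility, and the power statement is supplementary.

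**The concern.** This is the only power statement for the co-primary outcomes, and it ends in a claim of sufficient power. Its inputs are complete, so it can be checked, and with 28 completers per arm and an SD of change of 0.6 the answer should be well below 0.66 SD.

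A natural guess is that the gap is an undeclared allowance for clustering. The text gives no support for that. If clustering was simply forgotten, two errors pull in opposite directions: the unadjusted figure is too large for its inputs, while clustering and the small number of buildings raise the true detectable difference. The planned tests also treat residents as independent. If outcomes correlate within buildings, such a test does not hold the 5% level at which the power is quoted.

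**Working it through.** **Inputs, all from the power paragraph unless noted.** 70 enrolled; 20% dropout, so 70 × 0.8 = 56 completers, or 28 per arm (equal allocation, from the Aim 3 design); two-sided alpha 0.05; power 80%; SD of change 0.6 in units of the outcome SD; between-arm t-test of change.

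**SD of change.** With equal variances at the two times and r = 0.8, the SD of change is √(2(1 − 0.8)) = 0.632. The stated 0.6 may be a rounding of this. It also equals √(1 − 0.8²), the residual SD after baseline adjustment, which is not the planned analysis. Both values are carried below.

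**Formula.** Detectable difference = d × SD of change, where d is the standardized difference giving 80% power by the noncentral t distribution.

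**Attempt to reproduce 0.66.** With 28 per arm (54 df), d = 0.7624.
- SD 0.6: 0.7624 × 0.6 = **0.457**
- SD 0.632: 0.7624 × 0.632 = **0.482**

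The normal approximation, 2.8016 × SD × √(2/28), gives 0.449 and 0.474. The stated figure is not reproduced: 0.66/0.457 = 1.44 and 0.66/0.482 = 1.37. Power at 0.66 SD is 98.1% (SD 0.6) or 97.0% (SD 0.632).

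**Point values.** 0.66 × 2.7 = 1.78 and 0.66 × 2.2 = 1.45, so the conversions are sound and the error lies in 0.66 itself. From the inputs, SPPB is 0.457 × 2.7 ≈ 1.24 to 0.482 × 2.7 ≈ 1.30 points; ADL is 0.457 × 2.2 ≈ 1.01 to 0.482 × 2.2 ≈ 1.06 points.

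**Other readings tried.**

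| Reading | Detectable difference (SD) |
|---|---|
| No dropout, 35 per arm, SD 0.6 | 0.6794 × 0.6 = 0.408 |
| One-group change, 56 completers, SD 0.6 | 0.3811 × 0.6 = 0.229 |
| Alpha 0.025, 28 per arm, SD 0.6 / 0.632 | 0.506 / 0.534 |
| 90% power, 28 per arm, SD 0.6 / 0.632 (normal approximation) | 0.520 / 0.548 |
| Correlation and dropout both ignored (SD 1, 35 per arm) | 0.679 |
| Correlation ignored and test one-sided (SD 1, 28 per arm, normal approximation) | 0.665 |
| 14 completers per arm, SD 0.6 | 1.1001 × 0.6 = 0.660 |

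The last three come close, but each departs from the stated inputs. The exact match, 14 per arm, is what results if 35 residents (28 completers) are taken as the two-arm total. That is a likely origin, but the documents do not show it.

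**With clustering.** The documents give no ICC, so the values here are assumptions. Take 56 completers in 15 buildings (mean 3.73), split 7 and 8, hence 26.1 and 29.9 completers and 13 df. The design effect is DE = 1 + ((1 + CV²) × 3.73 − 1) × ICC, where CV is the coefficient of variation of building size. The detectable difference is 3.031 × SD × √(1/26.1 + 1/29.9) × √DE, where 3.031 is the noncentrality needed for 80% power with 13 df.

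| SD of change | CV | ICC 0 | ICC 0.05 | ICC 0.10 | ICC 0.20 | ICC at which it reaches 0.66 |
|---|---|---|---|---|---|---|
| 0.632 | 0 | 0.514 | 0.547 | 0.579 | 0.639 | 0.238 |
| 0.632 | 0.6 | 0.514 | 0.563 | 0.609 | 0.692 | 0.160 |
| 0.6 | 0 | 0.487 | 0.519 | 0.550 | 0.606 | 0.306 |
| 0.6 | 0.6 | 0.487 | 0.535 | 0.578 | 0.656 | 0.205 |

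Only one cell exceeds 0.66: 0.692 SD, or 0.692 × 2.7 = 1.87 SPPB points.

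**Level of the planned test.** The resident-level t-test was simulated under no effect (15 buildings of 3 to 4 completers, 20,000 runs). Type I error was 4.8%, 6.7%, 8.7% and 11.6% at ICC 0, 0.05, 0.10 and 0.20.

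**The case against.** The strongest reply is that little depends on this figure. The study is a pilot, its size rests on feasibility, and the follow-up trial is to be planned from the pilot's point estimates and standard deviations. Before clustering the error is conservative, because the trial can detect smaller effects than it claims. Even with clustering, 0.66 SD is exceeded only when three choices coincide: SD 0.632 in place of the stated 0.6, ICC 0.20, and marked variation in building size. At the stated SD of 0.6, every value up to ICC 0.20 stays below 0.66. One can add that resident-level testing after building randomization is a separate methods issue from a wrong number.

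Most of this stands, and it limits the weight of the point: the sample size is not in question, and 0.66 is probably conservative at modest ICCs. It does not rescue the figure, which is wrong on its own inputs and supports a claim of sufficient power for the co-primary outcomes. The two issues are distinct but meet in the remedy. A cluster-adjusted detectable difference describes the trial only if the analysis is cluster-adjusted too, and the planned tests are not.

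**Conclusion.** The concern holds. The plan's inputs give a detectable between-arm difference of 0.457 SD (SD of change 0.6) to 0.482 SD (0.632), not 0.66 SD. The point values for both co-primary outcomes carry the same error. This rests only on the stated inputs, equal arms and a two-sample t-test of change.

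Clustering by building is omitted from both the calculation and the tests. Under the assumed cluster model with SD 0.632, the detectable difference is 0.51 to 0.61 SD for ICCs of 0 to 0.10. It passes 0.66 only above an ICC of 0.24 (equal building sizes) or 0.16 (CV 0.6). With SD 0.6 those limits are 0.31 and 0.20. The stated figure is therefore likely, but not certain, to be conservative for this design, and the text gives a reader no means of telling.

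The power statement should be corrected. The sample size does not need to change.

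**What to change.** Keep 70 residents and rewrite the power paragraph so that it describes a between-arm difference in 2-month change, in two parts.

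1. **Before clustering.** With 28 completers per arm, 80% power at two-sided 0.05 is reached for about 0.48 SD (about 1.30 SPPB points) with an SD of change of 0.632. Quote 0.46 SD (1.24 points) only if the analysis is baseline-adjusted, for which 0.6 is the matching SD.
2. **After clustering.** Give a detectable difference with the assumed ICC, the building-size variation and the degrees of freedom stated. The values tabulated above are illustrations, not recommended assumptions.

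In the same section, replace the resident-level tests with a cluster-level or cluster-adjusted comparison, such as a t-test on building means or a mixed model with a building effect and small-sample degrees of freedom. Part 2 does not apply without this change.

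Two inputs should be confirmed at the same time. The 0.8 correlation is given for 6 months, but the outcome is at 2 months. The SD of 2.2 is given for an ADL/IADL score, whereas the Outcome measures section says: "We will also measure self-reported ability to perform 8 ADLs using the Yale ADL scale (range, 0-16").

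The cost is one rewritten paragraph, one changed test sentence and a stated ICC and building-size assumption. The test sentence is a change of method, so it should be settled before outcome data are compared. No additional residents are needed.
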